## 10 Statistical Considerations

For phase 2:

Successful adaptation will be measured on three levels: user-centered adaptation, technical integration, and workflow integration. Successful user-centered adaptation will be defined by qualitative analysis of the stakeholder interviews, usability testing, and evaluation of the adaptation design document. Key domains for evaluation will include: alignment with providers and organizational practices, perceptions of tool relevance, and feasibility of PAMS. Successful technical integration will be determined by the site's EHR team, who will test the reliability of the ddpp provider dashboard tool within the local EHR environment. Workflow integration will be evaluated via the "near live" usability. This data will be used to drive refinement of the tool during piloting. Using EHR reporting systems, reports will be built to assess provider dashboard use at each site. EHR reports will also be used to determine need for additional clinical care by clinic, urgent care or emergency department visits for pre-diabetes management.

For phase 3 RCT, please see the following sections.

### 10.1 Statistical and Analytical Plans

For phase 3:

CONFIDENTIAL

This material is the property of the NYU School of Medicine and NYU Langone Health. Do not disclose or use except as authorized in writing by the study sponsor Behavioral Intervention Template Version: 11 January 2019

We will conduct a 1-year pragmatic patient-level randomized trial comparing primary care practices (400 patients across multiple NYU Langone Health clinics) using: 1) the dDPP and 2) the dDPP + the dDPP-EHR tool suite.

## **10.2 Statistical Hypotheses**

Our primary hypothesis is that patients receiving the dDPP + the dDPP-EHR tool suite will have greater reduction in weight loss, greater increase in physical activity, and greater reduction in HbA1c.

Our secondary hypothesis is that patients receiving the dDPP + the dDPP-EHR tool suite will show higher engagement, assessed by number of logins and lessons completed. They will also report higher perceived provider involvement.

Our exploratory hypothesis posits that patients who engage more fully with the dDPP may engage in healthy behaviors more than those who are less engaged, which should lead to better weight loss outcomes. Hence, we hypothesize that patient engagement level can mediate the relationship between intervention and improvement in patient health outcome.

## **10.3 Analysis Datasets**

Our primary analyses will use intention-to-treat (ITT) analysis dataset of all randomized participants. Participant baseline demographics and clinical characteristics will be collected. Repeated measurements of participant weight, physical activity, and HbA1c level at baseline, 6 and 12 months from baseline, and patient engagement and perceived provider involvement at 6 and 12 months from baseline will also be collected. Long-formatted data will be stored and analyzed.

## **10.4 Description of Statistical Methods**

### **10.4.1 General Approach**

The study trial will utilize a patient-level randomized design, with 1:2 randomization of 432 patients from FGP clinics. Analyses will proceed under the intention-to-treat principle. The distribution of primary and other variables for enrolled patients will be summarized and compared by treatment group. Means and standard deviations will be calculated for continuous variables. Counts and frequencies will be calculated for categorical variables. The comparison of distributions by treatment group will be conducted by the independent two-sample t-test for continuous variables and the Chi-square test for categorical variables. We will use generalized estimating equations (GEE) to compare treatment arms with time as a fixed effect and practice as a random effect, to adjust for clustering of patients within practices; a major advantage of GEE is the sandwich variance estimator that is asymptotically robust to misspecification of the correlation structure. We will also report the intra-cluster correlation and time effect from the fitted model. For the second outcome of 7% weight-loss achievement, we will use a similar GEE model with a logit link function. Missing data frequently occur in pragmatic clinical trials with long follow-up. Standard GEE will be unbiased only if data are missing completely at random, which rarely occurs in practice. Thus, we will apply weighted GEE to accommodate the more realistic missing at random assumption. Due to the large number of clinics, providers, and patients, we expect balance by study arm over patient, provider, and clinic characteristics. In case of imbalance, however, we will investigate propensity score weighting to adjust the observed differences. In addition to estimating the effect of the dDPP on weight loss directly, we will explore the extent to which engagement with the program acts as a mediator. We will examine differences primary

CONFIDENTIAL

This material is the property of the NYU School of Medicine and NYU Langone Health. Do not disclose or use except as authorized in writing by the study sponsor Behavioral Intervention Template Version: 11 January 2019

outcomes and engagement measures using sex as a biological variable. Mediation analysis is a recommended approach to test potential causal pathways to support plausibility of outcome effects being causally associated with select interventions. We posit that those who engage more fully with the dDPP may engage in healthy behaviors more than those who are less engaged, which should lead to better weight loss outcomes. Here, we propose using a single mediator causal model approach with bootstrap-derived confidence intervals to measure dDPP effect on weight loss through the specific mechanism of patient engagement. The statistical programming language R will be used for all analyses and statistical significance will be defined using two-sided tests with alpha=0.05.

#### 10.4.2 Analysis of the Primary Efficacy Endpoint(s)

The table below outlines the study's main outcomes. Whenever possible, outcomes ascertained via automated or technology-facilitated objective approaches are used to enhance the pragmatic approach and minimize provider and patient burden; while weight and activity data will be collected more frequently (and be viewable to intervention patients and providers), 6- and 12- month assessments will be used to evaluate impact. To ensure data endpoint capture for weight and physical activity at 6 and 12 months, the study team will conduct outreach and troubleshoot with patients missing data at any of these intervals.

Construct	Measure	Data Source	Collected at (months)
Clinical outcomes	Weight reduction (kg)	Noom via wireless scale and survey, EHR	Baseline, 3, 6, 9, 12
	Physical activity (steps/day)	Noom via wireless pedometer	Baseline, 6, 12
	Hemoglobin A1C (%)	HbA1C home test kit and survey, EHR	Baseline, 6, 12
Engagement outcomes	Patient engagement (# dDPP logins) (# dDPP lessons completed)	Noom	6, 12
	Perceived provider involvement with dDPP progress	Patient portal 1-item survey	
Patient characteristics	Demographics, social determinants, and other baseline descriptive data	EHR	Baseline, 12

Change in body weight, a repeatedly measured continuous variable, will be our primary weight-based outcome. Secondarily, we will assess achievement of a 7% weight loss (the DPP weight goal), a binary outcome. Weight will be collected from the bluetooth linked wireless weight scale (Fitbit Aria or iHealth Fit/Nexus) that automatically reports weigh-ins to the Noom server. Mean steps per day, a repeatedly measured continuous variable, will be assessed using Fitbit or iHealth accelerometers integrated into the Noom platform. This objective device has been well-validated for the measurement of steps and found to be acceptable by study participants. HbA1C, the most common test used for prediabetes monitoring, will be assessed as a secondary outcome via HbA1C testing performed at home. HbA1C will be collected at baseline, 6 and 12 months. Patients will be sent a HbA1C testing kit upon enrollment, and prompted by

CONFIDENTIAL

This material is the property of the NYU School of Medicine and NYU Langone Health. Do not disclose or use except as authorized in writing by the study sponsor Behavioral Intervention Template Version: 11 January 2019

the study team at each time point to complete testing. HbA1C testing kits have been shown in prior studies to be safe and equivalent to laboratory testing, and are increasingly used in pragmatic digital studies to avoid unnecessary burden on participants.

For continuous outcomes including weight reduction, mean steps per day, and reduction in HbA1C level, we will use generalized estimating equations (GEE) to compare treatment arms with time and intervention as a fixed effect and practice as a random effect, to adjust for clustering of patients within practices. Participant demographic characteristics including age, gender, race/ethnicity and other potential confounders determined as a priori will be controlled for in GEE. We will also collect patient characteristics, such as demographic information, social determinants, and other baseline descriptive data, from the EHR. For the second outcome of 7% weight-loss achievement, we will use a similar GEE model with a logit link function. We will report the estimated effect of intervention and its associated 95% confidence interval calculated by using the robust variance estimator. We will also report the intra-cluster correlation and time effect from the fitted model.

Missing data frequently occur in pragmatic clinical trials with long follow-up. To supplement missing HbA1C and weight data from patients, we will conduct EHR data extractions. Our data analyst will run a query based on the appropriate time windows per patient to pull values and dates for HbA1C and weight, respectively. Standard GEE will be unbiased only if data are missing completely at random (MCAR), which rarely occurs in practice. Thus, we will apply weighted GEE to accommodate the more realistic missing at random (MAR) assumption. Due to the large number of clinics, providers, and patients, we expect balance by study arm over patient, provider, and clinic characteristics. In case of imbalance, however, we will investigate propensity score weighting to adjust the observed differences.

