### **10.5 Sample Size**

The primary hypothesis is whether weight change among patients affiliated with practices enabled with the dDPP-EHR tool suite is significantly different from weight change in patients using the dDPP in conjunction with usual care. Based on the ~40% increase in dDPP lesson completion (17 vs 12) among patients reporting high levels of provider engagement (post hoc analysis conducted by [name] on her GOALS dDPP), we estimated a range of expected effect sizes from 20-60% in lesson completion in the dDPP-EHR intervention arm (approximately equivalent to completing 2-8 more Noom dDPP lessons). We estimate that this increased lesson completion will translate into at least an additional 2.0 kg of weight loss in the intervention (dDPP-EHR) arm, a conservative estimate considering Noom's dDPP trial observed a 4 kg of weight loss difference (6.6 vs 2.4 kg) with the completion of 6 additional dDPP lessons and GOALS noted a 2.5 kg weight loss difference with 5 additional lessons completed. We estimate the 1 year weight loss will be 4.5 kg and 2.5kg for the dDPP-EHR and dDPP alone approaches, respectively. This is also conservative compared to the 6.2 vs 3.7 kg weight loss difference observed in the post-hoc analysis of GOALS dDPP participants reporting high vs. low provider engagement without any data integration (and the presumed enhanced lesson completion it would facilitate). We also assume a standard deviation of weight loss (at 1 year) of 5 kg based on data from Noom and another GOALS dDPPs. Empirical EHR data indicate that the average annual number of distinct eligible patients is approximately 200 per clinic. The proposed study sample provides 97% power to detect a conservative estimate of 30% increase in Noom dDPP session completion and a 2kg increased 12-month weight loss in the intervention arm if we have 200 patients/arm (a

CONFIDENTIAL

This material is the property of the NYU School of Medicine and NYU Langone Health. Do not disclose or use except as authorized in writing by the study sponsor Behavioral Intervention Template Version: 11 January 2019

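### The efficacy GEEs do not name each outcome's own baseline value as a covariate, which costs little precision for weight but more for HbA1c and steps/day

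*Combined protocol and SAP*

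**What the plan says.** Section 10.4.2 applies one GEE to the three continuous clinical outcomes: "For continuous outcomes including weight reduction, mean steps per day, and reduction in HbA1C level". Its terms are time and intervention as fixed effects, practice as a random effect, and these covariates: "Participant demographic characteristics including age, gender, race/ethnicity and other potential confounders determined as a priori will be controlled for in GEE". Section 10.4.1 describes the same GEE without a covariate list. Achievement of 7% weight loss gets a logit version. Neither section names baseline weight, steps/day or HbA1c as a covariate, and neither rules them out.

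The baseline values will exist. Section 10.3 lists "Repeated measurements of participant weight, physical activity, and HbA1c level at baseline, 6 and 12 months from baseline" and says that the data will be analysed in long format. The outcome table in 10.4.2 schedules a baseline for all three outcomes.

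Two further statements bear on which rows are responses. Section 10.4.2 says that the effect on weight and activity will be judged on the 6- and 12-month assessments. Sections 10.4.9 and 10.4.10 mention an intervention-by-time interaction only as something that may be considered. For chance imbalance, 10.4.1 and 10.4.2 offer to look into propensity score weighting.

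**The concern.** A participant's own baseline is usually the strongest single predictor of the follow-up value. In a randomised trial it is a prognostic covariate rather than a confounder, so a list framed as demographics plus confounders does not clearly take it in. Analysing raw change fixes the slope on baseline at one. That is unbiased, but it leaves in variance from regression to the mean and lets chance baseline differences reach the estimate. Analysing a follow-up level without baseline fixes the slope at zero and discards the information altogether.

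Steps/day is the outcome most exposed. It is worded as a level, while 10.2 hypothesises a greater increase in activity. The plan also does not say whether the baseline steps row belongs to the response. If it did, and the model held only main effects, the intervention coefficient would average in a baseline difference that randomisation makes zero on average.

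**Working it through.** **1. The plan's own power.** Inputs from 10.5: "We estimate the 1 year weight loss will be 4.5 kg and 2.5kg for the dDPP-EHR and dDPP alone approaches, respectively" (difference 2.0 kg); "We also assume a standard deviation of weight loss (at 1 year) of 5 kg"; "if we have 200 patients/arm". From 10.4.1: "statistical significance will be defined using two-sided tests with alpha=0.05". Power = Φ(difference/SE − 1.96), with SE = 5 × √(2/n).
- n = 200, 2 kg: SE = 0.50, power Φ(2.04) = 97.9% (stated 97%).
- n = 200, 1.75 kg: Φ(1.54) = 93.8% (stated 93%).
- n = 160, 2 kg: SE = 0.559, power Φ(1.62) = 94.7% (stated 94%).

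The figures reproduce. The 5 kg is the SD of a change score, so they already describe an analysis without baseline adjustment.

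**2. Assumptions below.** The documents give no r. It is read here as the correlation remaining after the demographic covariates. Clustering by practice is left out, SDs are taken as equal over time, and correlations between any two visits are taken as equal unless stated. Allocation is 144 v 288 (10.4.1 gives 1:2 of 432, and 432 − 144 = 288), with both messaging arms pooled, so 1/144 + 1/288 = 0.01042.

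**3. Change scores (weight, HbA1c).** The variance of the contrast is proportional to 2(1 − r) for raw change and 1 − r² with baseline as a covariate. The ratio is (1 + r)/2, a saving of (1 − r)/2.
- HbA1c: 25% at r = 0.5, 20% at 0.6, 15% at 0.7.
- Weight: assume loss is 3-5% of body weight and baseline SD is 15-22 kg. The share of the change variance explained by baseline is (loss fraction × baseline SD / 5)². This runs from (0.03 × 15/5)² = 0.8% to (0.05 × 22/5)² = 4.8%. The equal-variance formula gives a similar size: 5% at r = 0.90 and 2.5% at r = 0.95. At 200 per arm and 2 kg, power would move from 97.9% to 98.4% and 98.2%, under one point.

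**4. Steps/day as the 6/12-month mean level.** In units of SD² the variance is (1 + r)/2 without baseline and (1 + r)/2 − r² with it.

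| r | without | with | SE ratio | SE reduction |
|---|---|---|---|---|
| 0.5 | 0.75 | 0.50 | 0.816 | 18% |
| 0.6 | 0.80 | 0.44 | 0.742 | 26% |
| 0.7 | 0.85 | 0.36 | 0.651 | 35% |

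For illustration, assume an effect of 1000 steps, SD 3000 and r = 0.6.
- Without baseline: SE = 3000 × √(0.80 × 0.01042) = 274, power Φ(3.65 − 1.96) = 95%.
- With baseline: SE = 3000 × √(0.44 × 0.01042) = 203, power Φ(4.92 − 1.96) = 99.8%.

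With a smaller assumed effect of 0.3 SD, power is 92%, 91% and 89% without baseline at r = 0.5, 0.6 and 0.7, against 98.6%, 99.3% and 99.8% with it.

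**5. If the baseline steps row were a response.** True arm differences are 0, d and d at baseline, 6 and 12 months. With main effects only, complete data and an independence or exchangeable working correlation, the coefficient is (0 + d + d)/3 = 0.667d. Under an AR(1) structure with r = 0.5-0.7 it is 0.60-0.57d. Under independence with 80% and 70% follow-up it is (0.8 + 0.7)/(1 + 0.8 + 0.7) = 0.60d. In the step 4 example: SE = 3000 × √((1 + 2 × 0.6)/3 × 0.01042) = 262, power Φ(667/262 − 1.96) = 72%. If only 6 and 12 months are responses, the coefficient is d.

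**The case against.** The case against has four parts.

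- **The covariate list is open.** Unnamed a priori confounders could include baseline values. This is true, so the plan omits them rather than excludes them. But a list that is not given does not pre-specify anything.
- **Raw change is a valid randomised comparison.** Preferring baseline adjustment is a matter of efficiency, not the correction of a bias. This stands, and for the primary weight outcome the efficiency at issue is small. A reader might infer that the primary analysis is underpowered. The documents do not support that: 10.5 uses the SD of weight loss, and its figures reproduce.
- **Imbalance is not ignored.** Baseline values will be compared by arm, with propensity score weighting as a possible remedy. That remedy would be decided after the data are seen, in an unblinded trial. A named covariate needs no such decision.
- **The steps effect is not shown to be diluted.** From the long-format data in 10.3 and the main-effects model, a reader might infer that the planned steps estimate is a third too small, with power near 72%. The documents do not establish this. Section 10.3 describes what is collected and how it is stored, not the response vector, whereas 10.4.2 says that the 6- and 12-month assessments carry the evaluation. On that reading dilution is zero and the example's power is about 95%. Most of the gap between 72% and above 99% therefore comes from the assumed baseline row, not from the missing covariate.

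**Conclusion.** The concern holds as a loss of precision and a gap in specification. No section names the outcome's own baseline as a covariate, and naming it improves precision on every reading in which it is not already in the model. The size depends on correlations that the documents do not give: about 1-5% of variance for weight change, about 15-25% for HbA1c change at r = 0.7-0.5, and a standard error about 18-35% lower for steps/day at r = 0.5-0.7. Under the assumed 1000 steps, SD 3000 and r = 0.6, power for steps rises from about 95% to above 99%. The stated power for weight is not undermined.

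The two-thirds factor for steps is a conditional risk. It applies only if the baseline row is modelled as a response without an interaction, which the plan neither states nor excludes.

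**What to change.** In 10.4.1 and 10.4.2, state that:
- the responses in each continuous outcome model are post-baseline values only;
- each such model includes the participant's own baseline value of that outcome (weight, steps/day or HbA1c) as a covariate;
- the logit model for 7% weight loss includes baseline weight.

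This is a free improvement. It changes SAP wording only and needs no new data, visits or participants. It also settles which steps rows are responses and so removes the dilution risk.

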#### **10.4.6 Baseline Descriptive Statistics**

The distribution of baseline demographics and clinical outcomes will be summarized and compared by treatment group. Means and standard deviations will be reported for continuous variables. Counts and percentages will be reported for categorical variables. The comparison of distributions by treatment group will be conducted by the two-sample independent t-test (or its non-parametric counterpart, the Wilcoxon's rank-sum test, as appropriate) for continuous variables and the chi-square test (or the Fisher's exact test, as appropriate) for categorical variables.

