#### **10.4.8 Additional Sub-Group Analyses**

No sub-group analyses are planned.

The primary endpoint of weight loss will be analyzed using a two-sided Type I error rate of 0.05. Other outcomes are considered secondary outcomes and no adjustment is required.

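### Propensity weighting after an undefined baseline imbalance leaves the primary estimator open, and baseline weight is not among the covariates named for the primary GEE

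*Combined protocol and SAP*

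**What the plan says.** Section 10.4.2 sets out the primary analysis: a GEE with time and intervention effects, practice as the clustering unit, a robust variance, and weighting for data missing at random. It adjusts for age, gender, race/ethnicity and other confounders to be chosen in advance but not listed. It then adds: "In case of imbalance, however, we will investigate propensity score weighting to adjust the observed differences". Section 10.4.1 carries the same sentence, and section 10.4.3 applies the same handling of imbalance to the secondary endpoints.

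None of these sections defines imbalance, lists the variables for the propensity model, gives the form of the weights, says how they combine with the missing-data weights, or says whether the weighted estimate is primary or a sensitivity analysis.

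Baseline comparisons are planned as significance tests. Section 10.4.1 has "The comparison of distributions by treatment group will be conducted by the independent two-sample t-test for continuous variables", and section 10.4.6 has them "conducted by the two-sample independent t-test", with rank-based and categorical counterparts. Sections 10.3 and 10.4.2 list weight as measured at baseline, and section 10.4.2 makes change in body weight the primary outcome. Section 10.6.1 says that neither patients nor providers are blinded.

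**The concern.** In a randomised trial a baseline difference between arms is chance, unless randomisation has failed. A plan that adjusts only when a difference is noticed makes the estimator a function of that chance. With no definition of imbalance and no status for the weighted result, two analysts who both follow the text could report different primary estimates from the same data. Nothing says that the decision must be made before outcome data are seen.

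Contingent adjustment is also a weak use of baseline data. A prognostic covariate adjusted for in every trial improves precision in every trial; one brought in only after an observed imbalance does so only sometimes. Baseline weight is an obvious candidate, and the plan does not name it.

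**Working it through.** **1. The plan's own power figures.** Inputs from section 10.5: "We estimate the 1 year weight loss will be 4.5 kg and 2.5kg for the dDPP-EHR and dDPP alone approaches, respectively", a 2.0 kg difference; "We also assume a standard deviation of weight loss (at 1 year) of 5 kg"; 200 per arm; two-sided α of 0.05 (also section 10.4.8: "The primary endpoint of weight loss will be analyzed using a two-sided Type I error rate of 0.05"). Power = Φ(Δ / (SD·√(2/n)) − 1.96).

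- 200 per arm, 2 kg: 2 / (5·√(2/200)) = 4.00; Φ(2.04) = 97.9%. The plan says "The proposed study sample provides 97% power".
- 200 per arm, 1.75 kg: 1.75 / 0.5 = 3.50; Φ(1.54) = 93.8%. Plan: 93%.
- 160 per arm, 2 kg: 2 / 0.559 = 3.58; Φ(1.62) = 94.7%. Plan: 94%.

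All three reproduce, so the 5 kg SD is used below. This point does not change the stated sample size or power.

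**2. Standard error at the planned size.** Taking the 1:2 randomisation of 432 as 144 control against 288 pooled messaging patients (the plan does not state pooling), SE = 5·√(1/144 + 1/288) = 0.510 kg.

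**3. How often chance would produce an imbalance.** The plan gives no criterion. Assume, for illustration only, p < 0.05 on any of k independent baseline variables. For one two-group test per variable, the chance of at least one is 1 − 0.95^k. The columns for separate arms come from simulating correlated tests with 144 per arm.

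| k | Control v pooled | Each messaging arm v control | All three pairs |
|---|---|---|---|
| 3 | 14% | 25% | 32% |
| 5 | 23% | 38% | 48% |
| 10 | 40% | 61% | 73% |
| 20 | 64% | 85% | 93% |

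**4. What the switch would do.** Simulation: 144 v 288, SD 5 kg, 5 or 10 covariates together explaining R² of 0 to 0.30 of the outcome, three of them always in the model, inverse-probability weights on all of them when triggered, 4,000 trials per scenario.

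- Type I error: fixed model 4.8% to 5.6%; mechanical switch 4.0% to 5.8%; reporting whichever analysis is significant 5.8% to 6.6%.
- In triggered trials, the two estimates differed with an SD of 0.08 to 0.29 kg.
- With a true 1 kg effect, 10 covariates and R² of 0.10 to 0.30, the significance verdict differed in 12% to 21% of triggered trials.
- With 8 covariates, all weighting variables already in the outcome model and R² of 0.15 or 0.30, the SD of the difference fell to about 0.06 kg and the verdict differed in 3% to 4% of triggered trials.

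**5. Precision.** Take 8 covariates with total R² of 0.15 or 0.30, shared equally, three of them in the base model. Adjusting for a fraction f of that R² gives SE = 0.510·√(1 − f·R²). At a true effect of 1 kg (chosen because power is near 50% there, where differences show most), power = Φ(1/SE − 1.96).

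| R² | Three of eight (f = 3/8) | All eight (f = 1) |
|---|---|---|
| 0.15 | SE 0.496, power 52% | SE 0.471, power 57% |
| 0.30 | SE 0.481, power 55% | SE 0.427, power 65% |

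Simulating the same set-up gave 52% for the triggered switch against 55% for fixed adjustment at R² 0.15, and 55% against 64% at 0.30. The switch therefore recovers almost none of the available gain. The 95% half-width (1.96·SE) is 0.97 v 0.92 kg, and 0.94 v 0.84 kg.

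At the plan's own 2 kg effect the power gain is slight: Φ(2/0.496 − 1.96) = 98.1% v Φ(2/0.471 − 1.96) = 98.9%, and 98.6% v 99.7% at R² 0.30.

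**The case against.** The strongest reply is that the plan already fixes most of the primary analysis: model, time and intervention terms, core covariates and robust variance are named, and propensity weighting is only to be investigated. That wording fits a sensitivity analysis as well as a replacement. The reply is fair, but the plan does not say which is meant, and that is the gap.

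Secondly, if the weights use covariates already in the GEE, the switch hardly matters (step 4). That also stands. A variable outside the model would matter more, and neither list is closed.

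Thirdly, baseline weight could be among the unlisted confounders chosen in advance, and it enters the outcome through the change score. So its exclusion is not shown; it is only not named.

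Several stronger readings are tempting and should not be drawn:

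- A reader might infer that the baseline tests trigger the weighting, since section 10.4.1 also says "statistical significance will be defined using two-sided tests with alpha=0.05". No section makes that link. It is plausible because these are the only planned baseline comparisons, but the frequencies in step 3 remain conditional on it.
- A reader might say that two-sample tests cannot serve a three-arm trial. They fit if the two messaging arms are pooled, as the 1:2 ratio and the two-group hypotheses in section 10.2 suggest. Whether they are pooled is a separate question.
- A reader might say that the confidence intervals would be wrong because estimated weights are treated as known. The plan states no such variance method.

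**Conclusion.** The point holds as a gap in pre-specification. The primary estimator is not fully fixed, because an undefined imbalance may bring in propensity weighting with undefined status, and baseline weight is not named among the covariates.

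The cost is analytic flexibility and some lost precision. It is not bias, and the type I error figures do not support a claim of material inflation: a mechanical switch stays near 5%, and even free choice of the more favourable result reaches only about 6.6%.

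The sizes rest on assumptions that the documents do not supply: the number of covariates, R² between 0 and 0.30, a p < 0.05 trigger, and pooled messaging arms. The R² values describe a set of covariates, not baseline weight alone. The documents give no correlation between baseline weight and weight change, so its own contribution could be smaller. This is an improvement available at almost no cost, not a flaw that threatens the trial's conclusion.

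**What to change.** In sections 10.4.1, 10.4.2 and 10.4.3:

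- State that the primary GEE always adjusts for baseline weight, age, gender, race/ethnicity and a closed, named list of any other covariates, whatever balance is observed. For the other continuous outcomes, adjust for their own baseline value where one is collected (steps per day and HbA1c).
- Delete the propensity-weighting sentence, or label that analysis a sensitivity analysis and name its variables and form of weights.

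Optionally, in sections 10.4.1 and 10.4.6, report baseline data by arm as means, SDs and counts without significance tests. This is a reporting preference and changes no estimate.

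The cost is SAP wording, best settled before outcome data are seen. It needs no new data or participants, and gives up only the option to reweight the primary analysis after the fact.
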